3.3.4.2 Discontinuation of the trial by the sponsor

Boehringer Ingelheim reserves the right to discontinue the trial overall or at a particular trial site at any time for the following reasons:

1. Failure to meet expected enrolment goals overall or at a particular trial site
2. Emergence of any efficacy/safety information that could significantly affect continuation of the trial
3. Violation of GCP, the CTP, or the contract by a trial site or investigator, disturbing the appropriate conduct of the trial
4. The recommendation of the DMC that would require discontinuation of the trial due to an imbalance in benefit/risk
5. Discontinuation of the clinical development programme with afatinib in paediatrics.

Proprietary confidential information.

© 2017 **Boehringer Ingelheim International GmbH** or one or more of its affiliated companies. All rights reserved.

This document may not - in full or in part - be passed on, reproduced, published or otherwise used without prior written permission.

6. The primary analysis has been completed and all patients have either experienced progressive disease or are eligible to receive afatinib under the conditions indicated in [Section 3.3.4.1](#)

The investigator / the trial site will be reimbursed for reasonable expenses incurred in case of trial termination (except in case of the third reason).

Proprietary confidential information.

© 2017 Boehringer Ingelheim International GmbH or one or more of its affiliated companies. All rights reserved.

This document may not - in full or in part - be passed on, reproduced, published or otherwise used without prior written permission.

4. TREATMENTS

4.1 TREATMENTS TO BE ADMINISTERED

Patients will be treated with once daily oral dosing of afatinib.

Oral solid single-unit dosage forms represent stable and convenient formulation approaches and are therefore proposed for treatment of paediatric patients that are able to swallow them.

For younger children who cannot swallow the film-coated tablets, and for doses which cannot be achieved by the film-coated tablets, capsules and solvent for oral solution have been developed. This oral liquid formulation may also serve as alternative formulation for older paediatric patients who do not accept the film-coated tablets.

4.1.1 Identity of BI investigational product

Substance (INN) Afatinib
(Brand name): (Giotrif®, Gilotrif®)

Pharmaceutical form: Film-coated tablet

Source: Boehringer Ingelheim Pharma GmbH & Co. KG

Unit strength: 20, 30, 40 and 50 mg film-coated tablets (the dose of afatinib in the film-coated tablets is related to the free base equivalent to afatinib)

Route of administration: Oral

Posology: Once daily

Substance (INN) Afatinib
(Brand name):

Pharmaceutical form: Capsules and Solvent for Oral Solution

Source: Boehringer Ingelheim Pharma GmbH & Co. KG

Unit strength: 200 mg capsule to be dissolved in aqueous solvent (2 capsules per 100ml solvent), i.e. 4 mg/ml

Route of administration: Oral

Posology: Once daily

Proprietary confidential information.

© 2017 Boehringer Ingelheim International GmbH or one or more of its affiliated companies. All rights reserved.

This document may not - in full or in part - be passed on, reproduced, published or otherwise used without prior written permission.

4.1.2 Method of assigning patients to treatment groups

Patients who have given their informed assent/written consent and whose parent(s)/legal guardian(s) gave written consent will be enrolled sequentially. A **screening form** must be faxed or emailed to the sponsor as soon as written informed consent has been obtained. Recruitment will be competitive.

Patients who meet all eligibility criteria will be entered into the study. A **registration form** will be faxed or emailed to the sponsor for patients who meet the eligibility criteria prior to starting study treatment.

The screening form and the registration form will be used by the sponsor for tracking purposes (overall recruitment, dose cohort assignment, tumour type information)

During the dose finding part, a rolling 6 statistical design will be used for dose escalation ([R12-4744](#)). Treatment slots are assigned by the sponsor in close collaboration with the recruiting sites according to [Table 4.1.4.1:1](#). The sponsor will return the registration form for cohort confirmation.

The MTD expansion cohorts/Phase II part will recruit patients in a biomarker specific approach, see [section 3.3.2](#). For cohorts 1 to 4, ErbB deregulation in each patient's tumour sample must be confirmed centrally. For cohort 5, an analytical laboratory report to prove genomic, transcriptomic or proteomic ErbB alterations (which are not defined in [Tables 5.6:1 - 5.6:4](#)) must be provided prior to study entry. For the MTD expansion cohorts/Phase II part a high rate of screening failures is expected. Therefore a pre-screening informed consent may be used to allow collection of tumour tissue samples and minimum data for central assessment of ErbB deregulation (further details are explained in the pre-screening informed consent. Upon confirmation of positivity for selection biomarkers (see [Section 3.3.2](#)) and before to proceed with trial procedures, the informed consent/assent for trial entry must be signed.

Recruitment will be closely monitored by the sponsor and sites will be informed of global patient enrolment numbers on an ongoing basis. Recruitment will continue until confirmation is received that patients included are evaluable for MTD (dose finding part) and the minimum number of patients required for assessment of OR (MTD expansion cohorts/Phase II part) is reached (see [Section 3.3](#)).

Following registration, patients should begin protocol treatment within 7 days.

4.1.3 Selection of doses in the trial

The choice of afatinib dose levels for this trial follows current clinical development practice and regulation ([P96-1356](#)) taking into account the available strengths of the tablet formulation. Five dose levels are planned in this trial. They are based on the approved dose for adults of 40 mg and described in [Table 4.1.3:1](#).

(http://www.ema.europa.eu/docs/en_GB/document_library/EPAR_-_Product_Information/human/002280/WC500152392.pdf)
(https://www.accessdata.fda.gov/drugsatfda_docs/label/2016/201292s010lbl.pdf)

A recently published comparative analysis of paediatric dose finding trials of molecularly targeted agents with adults' dose finding trials by Paoletti et al ([R13-4734](#)) showed that the

Proprietary confidential information.

© 2017 Boehringer Ingelheim International GmbH or one or more of its affiliated companies. All rights reserved.

This document may not - in full or in part - be passed on, reproduced, published or otherwise used without prior written permission.

recommended Phase II dose for paediatric patients ranged between 90% to 130% of the BSA-adjusted adult dose for 70% of the trials. Due to conventional dose escalation, 63% of paediatric patients did not receive an optimal dose during Phase I. Toxicity profiles were very similar between children and adults. For EGFR targeted agents and dual HER2/EGFR inhibitors BSA adjusted paediatric MTDs ranged between 100% and 180% of RPIID or FDA approved dose ([R13-4734](#)). However, as afatinib has shown anti-tumour activity at doses between 20 – 50 mg in adults a starting dose at 80% level of the adult dose is chosen for safety reasons. Allometric scaling of the dose, based on BSA ([R13-5168](#), [R13-5170](#), [R13-5167](#), [P13-15789](#)), is proposed in the dose finding part to take allometric differences between children and adults into account. The dose escalation will start at 80% of the approved adult dose (estimated by allometric scaling) with escalation levels to 100%, 125% and 150%; in case 80% is exceeding the MTD, dose level -1 will allow dose de-escalation to 50%. For obese patients BSA may be derived based on ideal body weight per institutional standard.

Table 4.1.3:1 Target dose in child as a function of efficacious dose in adult and dose level

Dose level	Percentage of adult dose (%)	Equivalent pediatric dose mg/m ² *
-1	50	12
0	80	18
1	100	23
2	125	29
3	150	35

* for actual dose, please refer to [Table 4.1.4:1](#)

The dose finding part has been completed and the MTD was determined at 80% of the approved adult dose (estimated by allometric scaling based on BSA) ([c09990672-01](#)).

4.1.4 Drug assignment and administration of doses for each patient

Patients will be administered a single oral dose of afatinib each day. Treatment will be applied continuously until the development of progressive disease or unacceptable adverse events.

The medication should be taken at the same time each day (± 2 hours) without food (at least one hour before or at least three hours after a meal). If above time intervals cannot be adhered to in patients ≥ 1 year and < 2 years, time and type of food consumed within the critical application window for afatinib has to be recorded in the patient diary.

Missed doses of afatinib can be made up during the same day as soon as the patient remembers. However, if the next scheduled dose is due within 8 hours then the dose must be skipped and patients should take the next scheduled dose at the usual time. Patients with emesis must not take a replacement dose.

Proprietary confidential information.

© 2017 Boehringer Ingelheim International GmbH or one or more of its affiliated companies. All rights reserved.

This document may not - in full or in part - be passed on, reproduced, published or otherwise used without prior written permission.

Depending on age, BSA (see [Appendix 10.7](#)), dose strength and individual preference, afatinib film-coated tablets or liquid formulation prepared from afatinib capsules and solvent for oral solution may be applied.

Assuming comparable exposure for both formulations (see [Section 1.2](#)), the oral solution and the film-coated tablets may be used interchangeably when determining the MTD, in case of matching doses (deviation $\pm 10\%$) as specified in [Table 4.1.4.1](#). However, individual patients shall not switch between formulations as long as this is not necessitated by dose adaptations due to changing weight or BSA, or changes in the clinical health status or if patient adherence to treatment is otherwise endangered. **In any case, it must be attempted to keep all patients on their starting formulation for their first treatment cycle. This will be crucial for MTD determination.**

BSA has been recommended as the principal basis for drug dosage in the majority of chemotherapy regimens in adults and children ([R13-1191](#); [R13-1141](#); [P13-03365](#)).

For the current afatinib development in paediatric patients, allometric scaling was used to support estimation of a starting dose for different age groups based on the approved adult dose (40 mg).

Table 4.1.4: 1 Proposed afatinib dosing schedule for the Phase I/II

	Dose levels									
	Level -1 (50%)		Level 0 (80%)		Level 1 (100%)		Level 2 (125 %)		Level 3 (150%)	
BSA range (m ²)	AOS (mL)	Tablet (mg)	AOS (mL)	Tablet (mg)	AOS (mL)	Tablet (mg)	AOS (mL)	Tablet (mg)	AOS (mL)	Tablet (mg)
<0.40	1.0	-	2.0	-	2.5	-	3.0	-	3.5	-
[0.40 - 0.50[1.5	-	2.5	-	3.0	-	3.5	-	4.5	-
[0.50 - 0.65[1.5	-	2.5	-	3.5	-	4.0	-	5.0	-
[0.65 - 0.71[2.0	-	3.0	-	3.5	-	4.5	-	5.5	-
[0.71 - 0.79[2.0	-	3.5	-	4.0	-	5.0	-	6.0	-
[0.79 - 0.86[2.5	-	3.5	-	4.5	-	5.5	-	7.0	-
[0.86 - 0.93[2.5	-	4.0	-	5.0	-	6.0	-	7.5	-
[0.93 - 1[2.5	-	4.5	-	5.5	20	6.5	-	8.0	30
[1 - 1.08[3.0	-	4.5	20	5.5	-	7.0	30	8.5	-
[1.08 - 1.16[3.0	-	5.0	20	6.0	-	7.5	30	9.5	40
[1.16 - 1.28[3.5	-	5.5	20	6.5	-	8.5	-	10	40
[1.28 - 1.38[3.5	-	6.0	-	7.5	30	9.0	40	11	-
[1.38 - 1.49[4.0	-	6.5	-	8.0	30	10.0	40	12	50
[1.49 - 1.56[4.5	-	7.0	30	8.5	-	10.5	40	13	50
$\geq 1.56^*$	-	20	-	30	-	40	-	50	-	2 x 30

AOS: afatinib oral solution, 4 mg/mL

*Patients with a BSA ≥ 1.56 , who are not able to swallow film coated tablets can also receive oral solution

Study drug will be prescribed by the investigator and may be dispensed either by the investigator, site staff or affiliated pharmacy. Afatinib oral solution (capsules and solvent for

Proprietary confidential information.

© 2017 Boehringer Ingelheim International GmbH or one or more of its affiliated companies. All rights reserved.

This document may not - in full or in part - be passed on, reproduced, published or otherwise used without prior written permission.

oral solution) will be prepared preferably at the investigational site. After preparation, afatinib oral solution is stable for 4 weeks. At each course, the dose level of the drug must be checked and the patient will be re-supplied with a new bottle of freshly prepared afatinib oral solution.

Feeding tubes made of PVC and PUR have successfully been tested with Afatinib oral solution, i.e. they showed no negative influence on the intended dose of afatinib. The oral syringe (see [Section 4.1.6](#)) must not be used for rinsing the feeding tube.

Afatinib film-coated tablets should be swallowed with a glass of water and should not be chewed or crushed.

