© 2017 Boehringer Ingelheim International GmbH or one or more of its affiliated companies. All rights reserved.

This document may not - in full or in part - be passed on, reproduced, published or otherwise used without prior written permission.

- EGFR gene amplification (FISH): Either $EGFR/Cen7 \geq 2.0$ or $\geq 10\%$ of cells with ≥ 15 copies or $\geq 40\%$ of cells with ≥ 4 copies or gene cluster in $\geq 10\%$ of cells *and/or*
- HER2 gene amplification (DDISH): $Her2/CEP17 \geq 2.0$ *and/or*
- EGFR protein expression: H-score > 150 (membrane staining) *and/or*
- HER2 protein expression: H-score > 0 (membrane staining)

Inclusion will be based on biomarker assessment prior to inclusion, as detected by central laboratory analysis of tumour biopsy material

- Inclusion criterion #3: Patients aged between ≥ 1 to < 18 years
- Inclusion criterion #7: Archival and/or fresh tumour tissue available.

Inclusion criteria 2, 4, 5, 6, 8-12 apply as above

- Inclusion criterion #13: Patients with proven genomic, transcriptomic or proteomic ErbB alterations which are not defined in the above inclusion criterion #1 regardless of tumour histology (See [Section 5.6](#), [tables 5.6:1 to 5.6:4](#)).
- Inclusion criterion #14: Patients must have at least one measurable lesion according to the institutional response criteria for the given tumour type.

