Note that the Rolling 6 design allows enrolling up to 6 patients on each dose cohort. The first cohort of patients will start with dose level 0 (i.e. 80% of adult dose) as listed in [Table 4.1.3:1](#). As soon as at least two patients are treated at dose level 0, the dose level for the third and subsequent patients will be determined based on the number of patients determined to have experienced DLT, those determined without DLT, and those with DLT data pending for the first treatment course, as illustrated in the first row of [Table 4.1.4.1:1](#). For illustration purpose, an example (considering 4 patients treated on dose level 0) is given below:

- 1) If DLT data of all 4 patients are available and none of them observed with DLT, the dose level may be escalated and the 5th patient will be enrolled to dose level 1
- 2) If data is not yet available for one or more of the first 4 patients, or if one patient with DLT is observed, then the 5th patient will remain on dose level 0; the decision on further dose escalation or de-escalation will be made based on the rules illustrated for a 5-patient cohort
- 3) If more than 2 patients are observed with DLTs, the dose will be de-escalated and the 5th patient will be enrolled to dose level -1

If scenario 1) occurs, dose level 1 becomes dose 'd' in [Table 4.1.4.1:1](#). The process repeats after two patients are enrolled on dose level 1.

If scenario 3) occurs, dose level 0 exceeds the MTD, and dose level -1 is the lowest dose level allowed in this trial. Up to six patients will then be treated on this level, if $\leq 1/6$ patients with DLT, then dose level -1 will be the MTD; if ≥ 2 patients with DLT, then there will be no MTD.

Similarly, suppose the trial has been escalated to higher dose levels, e.g. dose level 3, and ≥ 2 patients had DLT, and if dose level 2 treated less than 6 patients previously, then the dose will be de-escalated to level 2 to fill up to 6 patients and the decision will be made according to the last column in [Table 4.1.4.1:1](#).

As shown in [Table 4.1.4.1:1](#), in order for a dose level to be the MTD, there must have been 6 patients treated on the dose level (at most one patient can have DLT) and the next higher dose level exceeded MTD (≥ 2 patients with DLT). The exception to this rule is if none of the 4 dose levels exceeds MTD, then dose level 3 will be MTD.

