10.7 BODY SURFACE AREA CALCULATION

The target dose of Afatinib has been calculated based on BSA derived from the Dubois and Dubois formula.

$$BSA = (W^{0.425} \times H^{0.725}) \times 0.007184$$

Whereas:

W is the weight is in kilograms

H is the height is in centimetres.

The paediatric dose was calculated as follows:

Dose child = Dose adult x (BSA child / BSA adult) considering BSA = 1.75 m² for adult

Proprietary confidential information.

© 2017 Boehringer Ingelheim International GmbH or one or more of its affiliated companies. All rights reserved.

This document may not - in full or in part - be passed on, reproduced, published or otherwise used without prior written permission.

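### Table 4.1.4:1, level 0 (the declared MTD): children with BSA 0.40 to <0.50 m² are assigned 10 mg, 109–137% of the formula dose, and no reason is given

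*Protocol*

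**What the plan says.** Protocol 4.1.3 sets the targets. Table 4.1.3:1, "Target dose in child as a function of efficacious dose in adult and dose level", gives 18 mg/m² at level 0 (80%) and 23 mg/m² at level 1 (100%). Its footnote reads "for actual dose, please refer to" Table 4.1.4:1, so the second table is the operative one.

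Appendix 10.7 gives the rule behind the targets: "Dose child = Dose adult x (BSA child / BSA adult"), with adult BSA taken as 1.75 m². The dose is therefore proportional to BSA.

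Table 4.1.4:1, "Proposed afatinib dosing schedule for the Phase I/II", turns this into volumes of a 4 mg/mL solution in 0.5 mL steps. At level 0, BSA 0.40 to <0.50 m² and BSA 0.50 to <0.65 m² both receive 2.5 mL.

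Protocol 4.1.3 reports that "the MTD was determined at 80% of the approved adult dose", which is level 0. Under 4.1.4.1, a level below the top one can be declared the MTD only if "the next higher dose level exceeded MTD".

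Protocol 2.3 says the MTD was established in children from 2 years. For the expansion part, 3.3.2 reads "Inclusion criterion #3: Patients aged between" 1 and under 18 years. The only special provision in 4.1.4 for ages 1 to under 2 begins "If above time intervals cannot be adhered to in patients" and concerns recording food intake, not dose.

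**The concern.** Level 0 is labelled 80% of the adult dose. One row of the operative table delivers clearly more than that, and it is the smallest closed BSA row, which the youngest children would occupy. The cell sets the starting dose and applies again whenever BSA is recalculated for a new course (Protocol 6.2.2).

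Two things are at stake. The first is safety: the level above was judged to exceed the MTD, and part of this row reaches that level's nominal mg/m². The second is interpretation: the expansion part is meant to confirm a safe recommended Phase II dose (Protocol 3.1), and any child in this row would count as treated at 80% while receiving more.

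**Working it through.** **Inputs.** Adult dose 40 mg (4.1.3); adult BSA 1.75 m² (Appendix 10.7); level fractions 0.5, 0.8, 1.0, 1.25 and 1.5 (Table 4.1.3:1); solution 4 mg/mL, BSA bands and volumes (Table 4.1.4:1).

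**1. Reproduce the stated targets.** Level 0: 0.8 × 40 / 1.75 = 18.29 mg/m² (stated 18). Level 1: 40 / 1.75 = 22.86 mg/m² (stated 23). Both agree.

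**2. The row in question.** 2.5 mL × 4 = 10 mg.
- At BSA 0.40: 10 / 0.40 = 25.0 mg/m², 137% of 18.29.
- Approaching 0.50: 10 / 0.50 = 20.0 mg/m², 109%.
- Midpoint: 10 / 0.45 = 22.2 mg/m², 121.5%. With the rounded target of 18 it is 123.5%.

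**3. All closed solution rows at level 0.**

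| BSA (m²) | mL | Midpoint, % of formula | Nearest 0.5 mL at midpoint |
|---|---|---|---|
| 0.40–<0.50 | 2.5 | 121.5 | 2.0 |
| 0.50–<0.65 | 2.5 | 95.1 | 2.5 |
| 0.65–<0.71 | 3.0 | 96.5 | 3.0 |
| 0.71–<0.79 | 3.5 | 102.1 | 3.5 |
| 0.79–<0.86 | 3.5 | 92.8 | 4.0 |
| 0.86–<0.93 | 4.0 | 97.8 | 4.0 |
| 0.93–<1.00 | 4.5 | 102.0 | 4.5 |
| 1.00–<1.08 | 4.5 | 94.7 | 5.0 |
| 1.08–<1.16 | 5.0 | 97.7 | 5.0 |
| 1.16–<1.28 | 5.5 | 98.6 | 5.5 |
| 1.28–<1.38 | 6.0 | 98.7 | 6.0 |
| 1.38–<1.49 | 6.5 | 99.1 | 6.5 |
| 1.49–<1.56 | 7.0 | 100.4 | 7.0 |

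Ten rows equal the nearest step at the midpoint, two are one step below, and only the first is above.

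**4. Is it rounding?** The formula volume at the midpoint is 18.29 × 0.45 / 4 = 2.06 mL, so the nearest step is 2.0 mL. It stays nearest up to BSA 2.25 × 4 / 18.29 = 0.492, which is (0.492 − 0.40) / 0.10 = 92% of the band. Ordinary rounding does not give 2.5 mL.

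**5. Is there another rule?** Take the formula volume at the upper BSA limit and round to 0.5 mL. This reproduces all ten cells of the two smallest rows (<0.40 and 0.40–<0.50, five levels each). For level 0 in this row it gives 18.29 × 0.50 / 4 = 2.29, rounded to 2.5 mL. Of the other 12 closed rows at level 0, 8 lie below that rule and 4 equal it.

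**6. Overlap with level 1.** 10 mg reaches the nominal 22.86 mg/m² at BSA 10 / 22.86 = 0.4375 or less, the lowest 37.5% of the band's width. The tabulated level 1 dose for this row is 3.0 mL = 12 mg, so level 0 is 2 / 12 = 17% below it.

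**7. Who could fall in the row.** These body sizes are assumptions, not from the documents. By the Appendix 10.7 BSA formula:
- 9 kg/74 cm: 0.414 m², 24.1 mg/m².
- 10 kg/75 cm: 0.437 m², 22.9 mg/m².
- 11 kg/82 cm: 0.486 m², 20.6 mg/m².
- 12 kg/86 cm: 0.522 m², outside the row.

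**8. With 2.0 mL (8 mg).** 8 / 0.40 = 20.0 mg/m² (109%), 8 / 0.50 = 16.0 (87.5%), midpoint 8 / 0.45 = 17.8 (97%).

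**The case against.** The strongest reply is that this is not an error. Ten matches out of ten with an upper-limit rule point to a deliberate convention for the smallest children, and no text prescribes a midpoint rule. The reason may lie in sources not supplied: the amendment log lists 4.1.3 and 4.1.4 among sections changed to meet the FDA Written Request, and the dose-finding results are in a separate interim report. This stands as far as it goes. A reader might infer a mistyped cell, but the pattern across both rows makes a banding choice more likely. It does not remove the inconsistency: whatever the convention, this row does not deliver the dose that the formula and the 80% label state.

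The table also tolerates deviation elsewhere. The 0.50–<0.65 row runs from 84% to 109% of target, and the 30 mg tablet at BSA 1.49 is 30 / 1.49 = 20.1 mg/m², 110%. That is fair, but those are extremes of rows or tablet bands, whereas here the lowest dose in the row is about 109%.

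Exposure may be slight. Ependymoma is the cohort most likely to include such children (25–40% diagnosed under 3 years, Protocol 1.1), but that is age at diagnosis. Entry requires recurrent or refractory disease after prior treatment, biomarker eligibility and a measurable lesion, so enrolled children will tend to be older. This stands.

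Weekly visits in course 1, DLT monitoring and mandatory dose reduction limit the consequences. They act after toxicity and do not correct a starting dose.

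**Conclusion.** The inconsistency is real and should be fixed. At the declared MTD, the 0.40–<0.50 m² row delivers 109–137% of the formula dose (midpoint 121.5%), equivalent to 88–109% of the adult mg/m² dose instead of 80%. This follows from the protocol's own formula and table and needs no outside assumption. Intent is unknown.

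Two stronger readings are not supported. A reader might infer that these children receive the level already found too toxic. Only those at BSA 0.40–0.4375 reach nominal level 1, the row midpoint (22.2 mg/m²) stays below it, and none receives the 12 mg tabulated for level 1. The DLT counts are not supplied. A reader might also infer that patients were overdosed. The documents do not say how many children fall in the row, and the number may be small or zero; nothing shows that the response analysis is affected. What gives the point weight is that the expansion part admits children from 1 year, below the age range in which the MTD was established.

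**What to change.** In Table 4.1.4:1, level 0, change the 0.40–<0.50 m² cell from 2.5 to 2.0 mL (8 mg; >16 to 20 mg/m²; 87.5–109% of target). Keep level -1 in that row at 1.5 mL. The formula volume there is 11.43 × 0.45 / 4 = 1.29 mL, so 1.5 mL is the nearest step (6 / 0.45 = 13.3 mg/m², 117%), while 1.0 mL would give 78%.

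If the higher level 0 dose is intended, give the reason, label the row with its actual mg/m² rather than 80%, and list the actual mg/m² and first-course DLTs for any child treated at BSA below 0.50 m².

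The open row below 0.40 m² (8 mg) is a weaker case: 109% of target at 0.40, which is ordinary rounding, rising to 125% at 0.35. Splitting it is optional and belongs with the sponsor's clinical pharmacology review.

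The cost is one cell in a short amendment and a letter to sites. The downside is that a later reduction from level 0 to level -1 in this row becomes 8 to 6 mg, 25%, instead of the present 10 to 6 mg, 40% (nominal step 80% to 50%, i.e. 37.5%).
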